# Aim 2: Determine the effect of NR (as compared to historical controls) on NAD(H) levels, mitochondrial function and its regulation through epigenomic modifications in the failing myocardium.

- a. Measure NAD+ and NADH levels in the blood and myocardium of the participants.
- b. Assess mitochondrial morphology and function in cardiac tissue using, respectively, EM and isolated mitochondria.
- c. Determine protein acetylation in the mitochondrial and non-mitochondrial compartments and changes in nuclear gene regulation.

# Aim 3: Test the hypothesis that NR improves mitochondrial function and reduces inflammatory response in HF patients receiving NR (as compared to historical controls).

- a. Measure mitochondrial function in peripheral blood mononucleated cells (PBMC).
- b. Determine the inflammatory response in PBMC.
- c. Compare effects on the circulating inflammasome vs. myocardial inflammation.

#### 1.3 Nicotinamide Riboside

NR is a relative of niacin, but a closer relative of nicotinamide which, unlike niacin, does

not induce flushing or pruritis and has no effect on lipid levels. NR does not induce insulin resistance or dysglycemia in mouse models. Thus, NR would potentially be cheap, safe, well-tolerated and readily available.

#### 2. Study Objectives

Enroll 5 participants undergoing elective LVAD placement to study the effects of NR on whole blood and myocardial NAD+ levels, as well as on measures of PBMC and cardiomyocyte mitochondrial function. The effects of NR on blood and myocardial markers of inflammation also will be assessed. Blood and myocardial tissue collected previously from individuals at the time of LVAD implantation will serve as historical controls.

#### 3. Study design

#### 3.1 Design Overview

This study is a single-center study to compare myocardial NAD+ level and other mitochondrial endpoints from NR administration with baseline untreated patients.

#### 4. Study Population

#### 4.1 Eligibility

**4.1.1.** Inclusion Criteria:

- Diagnosis of advanced heart failure.
- Planned elective LVAD implantation surgery with patient agreements for candidacy in place as required by UWMC.
- Hospital inpatient at time of enrollment.
- Ability to undergo Study procedures.
- Willingness/ability to provide informed consent.

#### 4.1.2. Exclusion Criteria:

- Current smoking
- Receiving certain concurrent supplements (to be determined at discretion of the PI). Note that UWMC Nutrition Care standards call for a general multivitamin (1 tab PO daily) as part of the advanced heart failure therapy (AHFT) work-up.
- Known allergies to niacin or nicotinamide.
- Hepatic, renal, endocrine, or neurological disease that disqualify them from consideration for LVAD implantation.
- Inability to perform Study visits or procedures.
- Unwillingness/inability to provide informed consent.
- Women who are currently pregnant or who wish to become pregnant over the course of the study follow-up are not allowed to join this study. This exclusion is built into the LVAD candidate selection process.

#### 4.2 Discontinuation of subjects from study treatment

This is a study of a nutritional supplement. Two published trials of NR administration in healthy participants did not show any major adverse effects. We also will monitor for worsening in signs and symptoms of heart failure, by asking about worsening of dyspnea, dyspnea on exertion, orthopnea, paroxysmal nocturnal dyspnea, arrhythmia/palpitations or edema.

(Airhart S, PLOS ONE 2017, Mertens CE Nature Communications 2018).

#### 4.3 Subject screening and identification

Prospective, eligible participants will be identified from the medical record from among patients with advanced heart failure who are planned to undergo LVAD implantation. If eligibility is confirmed, they will be contacted in person to determine their interest in enrolling into the Study. Each subject will receive a unique study ID. Once assigned to a subject, the subject's ID will not be re-used.

#### 5. Treatments

At the AHFT Thursday meeting, if the committee decides that a participant is to receive an LVAD, he or she will be prescribed NR according to the following administration schedule: Dose Escalation

Day 1: 250 mg (1 capsule) twice daily (total daily intake = 500 mg)

Day 2: 500 mg (2 capsules) twice daily (total daily intake = 1000 mg)

Day 3: 1000 mg (4 capsules) twice daily (total daily intake = 2000 mg)

#### Dose Maintenance

Day 4: 1000 mg (4 capsules) twice daily

Day 5-21 as applicable thru Day Before Surgery: 1000 mg (4 capsules) twice daily

#### Washout

Day of LVAD Surgery and/or Day 22: None

#### 6. Procedures

#### 6.1 - Identification of participants and consent

Based on the list of patients who are to be discussed at the Thursday Advanced Heart Failure Therapy (AHFT) meeting, potential research participants who are likely to receive an LVAD will be approached and, if interested, consented (please see separate consent form).

#### 6.2 – Study enrollment and follow-up

In-hospital Visit (Day 1)

- Demographic information, medical history, physical examination, current medical treatments
- Labs obtained as a part of routine inpatient heart failure clinical care: CBC with WBC differential and platelets, serum chemistry panel (sodium, potassium, chloride, glucose, blood urea nitrogen and creatinine), AST and ALT
- Additional Study blood collection: (20mL):
  - 10mL EDTA tubes for PBMC isolation
  - 10mL acid-citrate-dextrose (ACD)-containing tube for NR and NAD+ assays
- Eligible participants will begin NR administration

#### In-hospital Visit (Day 2)

• Demographic information, medical history, current medical treatments

- Labs obtained as a part of routine inpatient heart failure clinical care: CBC with WBC differential and platelets, serum chemistry panel (sodium, potassium, chloride, glucose, blood urea nitrogen and creatinine), AST and ALT
- Record of adverse events, if any

## Pre-LVAD implantation Visits (Day 2 or later; starting at least 2 days prior to LVAD implantation surgery)

- Day 2+:
  - Medical history, physical examination, current medical treatments
  - Labs obtained as a part of routine inpatient heart failure clinical care: CBC with WBC differential and platelets, serum chemistry panel (sodium, potassium, chloride, glucose, blood urea nitrogen and creatinine), AST and ALT
  - Record of adverse events, if any
  - Day 3+:
    - Labs obtained as a part of routine inpatient heart failure clinical care: CBC with WBC differential and platelets, serum chemistry panel (sodium, potassium, chloride, glucose, blood urea nitrogen and creatinine), AST and ALT
    - Record of adverse events, if any
    - Subjects then will receive the last 1000 mg dose of NR at 8pm.
- Day 4 (If NOT Day of Surgery):
  - Medical history, physical examination, current medical treatments
  - Labs obtained as a part of routine inpatient heart failure clinical care: CBC with WBC differential and platelets, serum chemistry panel (sodium, potassium, chloride, glucose, blood urea nitrogen and creatinine), AST and ALT
  - Record of adverse events, if any
  - Additional Study blood collection (20mL):
    - 10mL EDTA tube for PBMC isolation
    - 10mL ACD tube for NR and NAD+ assays

(1		(LV	line AD "S luled) Titration ↓ ↑ Daily fro 250→500→1 mg BID	y from Cont. 0→1000 1000		NR Day of	
	Day:	¥ 1	2	¥ Л		▼ (Varia	ble)
		1	2			Pre-O	
	Procedures: History	х	x	х		х	
Safety and Tolerability	Labs	x		X		x	
Salety and Tolerability	Disp Meds	x		x			
Peripheral Blood Effects	NR/NAD+ Levels PBMC Mitochondrial Function			x x		x x	
Myocardial Effects	NAD+/NADH Levels Mitochondrial Function Epigenetic Modifications						x x x
Inflammation/ Inflammasome	Circulating Inflammasome Myocardial Inflammatory Profil	 e				х	x

Day of Surgery

- Medical history, physical examination, current medical treatments
- Routine pre-operative labs
- Additional Study blood collection (20mL):
  - 10mL EDTA tube for PBMC isolation
  - 10mL ACD tube for NR and NAD+ assays
- In the operating room, myocardial samples from the LV apex (removed as an integral part of the LVAD implantation surgery:
  - Flash-frozen in liquid nitrogen for subsequent NAD+/NADH assays
  - Fresh samples for immediate processing for cardiomyocyte mitochondria isolation

If a subject has been enrolled as an inpatient, but needs to be discharged home due to a delayed LVAD surgery, IDS will dispense the study drug as discharge medication for a duration up to 7 days to bridge to the readmission. The patient will be called daily to assess for any adverse reactions to the study drug as an outpatient. Laboratory testing may be ordered per physician's discretion.

#### 6.3 – Specimen Destinations

- Whole blood NAD+/NADH levels [name] Pharmacokinetics Lab at the UW Health Sciences Building.
- Fresh tissue mitochondrial purification and functional (Seahorse®) assay, Seahorse [name] Lab at South Lake Union (SLU).
- Frozen mitochondrial ROS and DNA copy number, protein acetylation pattern (myocardium and PBMC) [name] Lab at SLU.
- Inflammatory response in PBMC and effects on the circulating inflammasome vs. myocardial inflammation [name] Lab at SLU.

#### 6.4 – Safety and adverse effect monitoring

Participants will have a structured history to enquire as to potential side effects and "safety" lab panel on Day 3. In addition, participants already hospitalized will have daily labs. Those not hospitalized at the time of enrollment also will have additional "safety" labs at the time of admission for the elective LVAD procedure (1-2 days prior to the LVAD implantation surgery). While the patient is inpatient, the chart will be reviewed daily to monitor for any potential adverse effects from NR administration. 4 weeks after the last dosing of the study drug, the subjects will be interviewed either in person or by phone to ask for any adverse effects or discomfort that they may have experienced during NR administration. The patient will be called daily to

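### The interview 4 weeks after the last dose asks only about effects during dosing, so the readable text sets no active adverse-event collection between post-operative discharge and that interview

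*Protocol*

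**What the plan says.** **When dosing stops.** Protocol Section 5 continues the maintenance dose "Day 5-21 as applicable thru Day Before Surgery". The washout line that follows reads "Day of LVAD Surgery and/or Day 22: None". For a participant who has surgery, the last dose therefore falls on the day before.

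**The contact after dosing.** Section 6.4 states: "4 weeks after the last dosing of the study drug, the subjects will be interviewed either in person or by phone". The purpose given is "to ask for any adverse effects or discomfort that they may have experienced during NR administration".

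**Collection in hospital.** Section 6.4 also states: "While the patient is inpatient, the chart will be reviewed daily to monitor for any potential adverse effects from NR administration". This is not restricted to the stay before surgery.

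**Collection outside hospital.** Section 6.2 covers the participant who "needs to be discharged home due to a delayed LVAD surgery" and is given drug to bridge to readmission. For that case it says: "The patient will be called daily to assess for any adverse reactions to the study drug as an outpatient".

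**A sentence that breaks off.** Section 6.4 ends, in the text supplied, with "The patient will be called daily to" and nothing more.

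**Other provisions.** Section 6.2 lists adverse-event recording only at visits before surgery. Section 7 says in general terms that health-status and medication data are gathered over the whole study, but names no contact and no time window. Section 12 has the DSMB review safety as each of the 5 participants completes the study.

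**The concern.** The protocol arranges to speak to each participant about four weeks after the operation, then limits the stated question to the period before it. Staff who follow the wording would not ask about an event that began after the last dose, even though they are in touch with the participant at the right time to hear of it.

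What is at stake is how complete the safety record given to the DSMB will be. The board looks at each participant separately, and the pilot is meant to show feasibility for a larger application (Section 1.2), so its safety record is likely to be relied on later. If serious events after discharge are recorded only when someone happens to mention them, the absence of a report cannot be read as the absence of an event.

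**Working it through.** The plan states no figure on this point, so there is none to reproduce. The check sets each adverse-event provision against the dosing calendar and then counts days.

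**Step 1. What covers which period**

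| Period | Provision | Active collection? |
|---|---|---|
| Dosing, in hospital | Adverse-event records at visits, Day 3 safety panel, daily chart review (Sections 6.2, 6.4) | Yes |
| Dosing, at home before a delayed operation | Daily calls (Section 6.2) | Yes |
| After the last dose, still in hospital | Daily chart review (Section 6.4) | Yes |
| After post-operative discharge, up to the interview | Interview, but its question stops at the end of dosing; general statement in Section 7 with no contact or window | None in the readable text |

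**Step 2. Inputs**

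- Last dose: the day before surgery (Section 5).
- Interview: 4 weeks after the last dose (Section 6.4), which is 4 x 7 = 28 days.
- Earliest surgery: Day 5 (Aim 1), so the earliest last dose is Day 4. Dosing is capped at 21 days (Aim 1).
- Post-operative stay, L days: not given.

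**Step 3. Reach of the question itself**

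Days since the last dose that fall inside the question as worded: 0 of 28. As a share of the whole span from first dose to interview, the part outside the question is 28 / (dosing days + 28):

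- shortest dosing: 28 / (4 + 28) = 28 / 32 = 87.5%
- longest dosing: 28 / (21 + 28) = 28 / 49 = 57.1%

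These shares describe the wording of one question. They do not measure total safety coverage, because chart review fills part of the 28 days.

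**Step 4. Length of the uncovered period**

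Surgery to interview = 28 - 1 = 27 days. With chart review running for L days after surgery:

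gap = max(0, 27 - L)

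- L of 27 or more: gap = 0 days
- L close to 0: gap just under 27 days

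The upper end is an arithmetic limit. Nothing in the documents suggests a post-operative stay that short.

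**Step 5. Participants who reach the dosing cap without surgery**

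Aim 1 excludes them from the study, so the 27-day count does not apply to them. If they are still interviewed, the question is limited in the same way.

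**The case against.** Four points can fairly be made on the other side.

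1. **The argument is from absence, in a section that is cut off.** The lost words come straight after the interview sentence and concern contact with the participant. Their opening matches the call sentence in Section 6.2, which belongs to the delayed-surgery case, so they probably repeat it. That cannot be confirmed. This stands as a limit on the finding, and the loss of text is not itself a fault in the plan.

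2. **Other provisions are broad.** Section 7 speaks of health-status data over the whole study, and Section 12 lets the DSMB ask for further side-effect data. Neither sets a contact, a question or a window after discharge. They soften the point without closing the gap.

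3. **The gap may be small or nil.** This stands. L is unknown, and a long post-operative stay removes the gap altogether. An attempted interview would also reveal a death, and a participant may volunteer an event.

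4. **Asking about the exposure period is a legitimate choice in a short, open-label pilot.** Events after major surgery with no concurrent control are hard to attribute, and no passage promises all-cause follow-up. This is why the point is an inexpensive improvement and not a contradiction in the plan. Difficulty of attribution is a reason for the DSMB to read such events in context; it is a weak reason not to ask.

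A reader might infer that nothing is collected after surgery. The documents do not support that, because chart review continues for as long as the participant is an inpatient.

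**Conclusion.** The point holds in a limited form. The only scheduled contact after dosing is worded to exclude all 28 days since the last dose, and the readable text sets no active collection from post-operative discharge to that contact. The uncovered period is max(0, 27 - L) days, anywhere from zero to just under 27.

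This rests on four assumptions: surgery follows the last dose by one day; the interview takes place on time; daily chart review continues through the post-operative stay as its wording allows; and the truncated sentence in Section 6.4 does not supply the missing collection.

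Two further inferences should not be drawn. The first is that serious events will in fact be missed: the documents give neither the length of stay nor any event rate, so no likelihood can be attached. The second is that Section 12 names myopathy as a domain for which nothing is measured. The safety panels and structured history are not itemised, adverse-event records are open-ended and the DSMB charter is not supplied. The symptoms listed in Sections 4.2 and 8 are heart-failure symptoms, so the lack of a muscle item there shows nothing.

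The change is worth making because it is cheap and alters a stated rule on what safety data are gathered.

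**What to change.** In Section 6.4, reword the existing 4-week contact and add a medical record check, so that together they record all deaths and serious adverse events from first dose to 4 weeks after the last dose, whatever cause is assigned. In Section 12, state that these data form part of the per-participant DSMB review and that no earlier review waits for them. This matters because the study completion that triggers each review is not defined relative to the interview. The sponsor should also check the full final sentence of Section 6.4 against the source document.

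**Cost.** One wider question and one record check for each of 5 participants, at a contact already planned. No visit or blood draw is added, and dosing is untouched. The drawback is that expected surgical events will be recorded and will need context when the DSMB reads them.

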#### 7. Sources of Materials

Data will be collected throughout the study from participants on their health status and concomitant medications. Clinical, demographic and laboratory values collected as a part of the Study will be stored in the multidimensional, REDCap database. All lab samples will be identified by a study number only. Individually identifiable data is recorded in individual study charts for each participant, and in the password-protected REDCap study database. Individually identifiable data will be accessible only to the study investigators.

#### 8. Potential Risks

Participants may experience discomfort and bruising from blood draws. Rarely, an infection could develop.

This is a study of a nutritional supplement. Two published trials of NR administration in healthy participants did not show any major adverse effects. We also will monitor for worsening in signs and symptoms of heart failure, by asking about worsening of dyspnea, dyspnea on exertion, orthopnea, paroxysmal nocturnal dyspnea, arrhythmia/palpitations or edema.

#### 9. Adequate Protection Against Risk

Recruitment and Informed Consent. Recruitment for this proposed study will be conducted according to the IRB policies at the University of Washington, as well as HIPAA policies. Potential study participants will be identified under HIPAA waiver by chart review. Their cardiologist will approve the approach before researcher contact. Potential participants will be contacted by phone using the approved phone script, or seen in person if at the clinic or a hospitalized inpatient. Only if the participant expresses any interest will we continue study recruitment. Study staff will explain the study's purpose and design and what would be required of participants. Then, the informed consent process will be conducted by an investigator or a study coordinator. Participants will be encouraged to ask questions and to share the information with their regular doctor. A copy of this consent will be given to the participants; the original will be placed in the participant's study chart.

Protection Against Risks. All access to individually identified participant data is limited to the investigators who are directly involved in this research study, the clinical research staff of the Translational Research Unit during the subjects' visits, and the UWMC Research Testing Service. Study charts and password-protected databases are confidential and are not released to outside parties except at the participant's request. All blood samples for laboratory analysis outside UWMC are ONLY identified by a study number. The Study charts containing paper forms will be stored in the locked file cabinets in the research clinics or offices where they only can be accessed by the investigators. Each participant's personally-Identifiable information in the study database and used to perform data entry and linking.

Notification of Participants and Their Physicians. A participant's primary cardiologist (or cardiology attending physician if hospitalized at time of discovery) will be any laboratory abnormalities develop. We will leave the further clinical follow-up and treatment plans to be made by the participants' physicians. Participants will not be notified of the results of other laboratory studies performed specifically for this Study.

#### 10. Potential Benefits of Research to the Participant and Others

Minimal. Although individual participants may benefit from this study by being on a nutritional supplement that has shown some promise in animal models of heart failure, it is unlikely that a short-term NR administration will yield any substantial clinical improvement or worsening in their clinical status.

#### 11. Importance of the Knowledge to be Gained

To our knowledge, no data exist regarding whether orally administered NR increases NAD+ levels or improves mitochondrial function in human myocardium. Therefore, we propose a trial to test the effects of NR on NAD+ levels and mitochondrial respiration in myocardium of advanced heart failure patients undergoing elective LVAD implantation

surgery. Secondarily, we plan to determine, using samples obtained at surgery, whether whole blood NAD+ levels and PBMC mitochondrial function correlate with, respectively, myocardial NAD+ levels and myocardial mitochondrial function.

#### 12. Data Safety Monitoring Board

The Data Safety Monitoring Board (DSMB) previously constituted for our on-going NR in Heart Failure Study *will amend its Charter* to provide oversight of this proposed Pilot Study. Safety reviews will be performed after Study completion by EACH of the 5 planned participants receiving NR. Safety data will include pre-specified evaluation of parameters for blood glucose, myopathy, hepatotoxicity, renal function as well as signs/symptoms of heart failure, or other possible clinical side effects, as requested by the DSMB. The threemember, Study DSMB Roster is provided below.

[name]. (Chair)
 Director, Clinical Trials Service Unit and Professor of Medicine (Cardiology)
 University of Washington School of Medicine

## Statistical Analysis Template

ClinicalTrials.gov

Statistical Analysis Overview	* Comparison Group Selection ①	Arm/Group 1 Arm/Group 2 Arm/Group 3
	Comments (2)	We performed a Pre- and Post-NR intervention comparison
	* Type of Statistical Test	(Select One)SuperiorityEquivalenceNon-inferiorityOther (for example, single group or other descriptive analysis)
	[*] Comments ③	
Statistical Test of Hypothesis	[*] P-Value (if applicable)	0.0405 (calculated value, not the a priori threshold for statistical significance)
	Comments (2)	We performed a pairwise 2-tailed student's T-test to compare the Pre-NR and Post-NR PBMC Maximal Respiration
	[*] Method (required if p-value entered)	(Select One)ANCOVAFisher ExactMixed Models Analysist-Test, 1-SidedANOVAKruskal-WallisRegression, Coxt-Test, 2-SidedChi-SquaredLog RankRegression, LinearWilcoxonChi-Squared, CorrectedMantel HaenszelRegression, Logistic(Mann-Whitney)Cochran-Mantel-HaenszelMcNemarSign TestOther ()
	Comments (2)	
Method of Estimation	[*] Estimation Parameter (if applicable)	(Select One)Cox Proportional HazardMean Difference (Net)Odds Ratio, LogSlopeHazard Ratio (HR)Median Difference (Final Values)Risk Difference (RD)OtherHazard Ratio, LogMedian Difference (Net)Risk Ratio (RR)()Mean Difference (Final Values)Odds Ratio (OR)Risk Ratio, Log
	Estimated Value	(calculated value)
	Confidence Interval (if applicable)	Level:  % Confidence Interval    Number of Sides: (Select One)  2-sided    Lower Limit:
	Parameter Dispersion	Type: (Select One)  Standard Deviation  Standard Error of the Mean    Value:
	Estimation Comments (2)	
Other Statistical Analysis ④		

\* Required [\*] Conditionally required

① Use the checkboxes to select the Arms/Groups (pre-populated from the Outcome Measure) involved in the statistical analysis.

(2) (Optional) Include any relevant information about the row above (e.g., the null hypothesis, details of the power calculation, adjustment for multiple comparisons, the *a priori* threshold for statistical significance, the direction of the comparison). Do not include written results or conclusions.

③ If a non-inferiority or equivalence analysis, information on the definition of the non-inferiority or equivalence margin is required.

(4) If the statistical analysis cannot be submitted using the Statistical Test of Hypothesis or Method of Estimation options, provide a description and the results of the scientifically appropriate test of statistical significance.

